### 10.3.9 Adverse Events (AE)

Adverse events will be coded using the MedDRA coding dictionary. A listing of all events, with seriousness, severity, relationship, sequelae and begin and end times will be provided. Narratives for any serious adverse events will be provided.

Deaths, serious adverse events (SAEs), and AEs leading to discontinuation of trial medication will be summarized by primary system organ class (SOC) and preferred terms. Listings will be provided.

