Once the RP2D is defined, intra-patient dose escalation to the R2PD will be allowed after a patient has completed at least 1 cycle at their assigned dose and only if the patient has experienced no toxicity above Grade 1, upon request by the PI and discussion with the Medical Monitor and the Sponsor.

Table 1: Summary of Dose Escalation

Single Patient Cohorts	
Observed Safety Outcomes	Action
AEs \leq Gr 1	
 Continue testing with single patient cohorts Escalate by 100% to next dose level
One AE \geq Gr 2 (excluding alopecia or diarrhea)	
 Expand current and subsequent cohorts to \geq 3 patients Escalate by \leq 50% to next dose level
1 DLT	
 Expand cohort up to 6 patients
Standard Escalation Cohorts (3–6 patients)	
Observed Safety Outcomes	Action
No DLTs	
 Escalate by \leq 50% to next dose level
1 DLT in 3 patients	
 Expand cohort up to 6 patients
1 DLT in 6 patients	
 Escalate by \leq 50% to next dose level
$>$ 1 DLT in \leq 6 patients	
 Stop dose escalation

When more than 1 DLT occurs in \leq 6 patients in a dosing cohort, dose escalation will be stopped and this dose level will be identified as a non-tolerated dose. Doses between the non-tolerated dose and the preceding lower dose, where \leq 1 DLT occurred, may be explored to define the MTD.

In Part 2 – Cohort-expansion Phase, an additional (approximately 105) patients with particular tumor types and/or cancers harboring specific genetic mutations (as specified in patient groups 1-7 below) will be recruited for treatment at the RP2D. Patients must have measurable disease by RECIST 1.1. Patients will receive twice daily oral doses of BVD-523 in 21-day treatment cycles until disease progression, unacceptable toxicity, or another withdrawal criterion is met. Treatment cycles will occur consecutively without interruption except when necessary to manage toxicities. Intra-patient dose modifications are allowed, including dose reductions/interruptions as needed and re-escalations up to and including RP2D, at Clinical Investigator’s discretion.

- Group 1: Patients with BRAF mutated cancer, except those with colorectal or non-small cell lung cancers, not previously treated with BRAF and/or MEK inhibitors; $n \leq 15$

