8.7 TREATMENT COMPLIANCE

Patients will take BVD-523 orally twice daily for 21-day cycles until disease progression, unacceptable toxicity, or a clinical observation satisfying another withdrawal criterion is noted. Patients may be treated beyond disease progression for additional 21-day cycles at the Investigators discretion. However it is particularly important in patients for which FDA approved BRAF and/or MEK inhibitors are indicated that BVD-523 treatment NOT be continued beyond tumor progression. Treatment cycles will occur consecutively without interruption, except when necessary to manage toxicities. No intra-patient dose escalation was permitted under the original protocol or the first two amendments. Under amendment three, some intra-patient dose escalations were allowed. Under amendment four, intra-patient dose escalations are only allowed to bring subjects to the RP2D (after it is identified), if deemed medically appropriate and if the subject has not experienced any toxicity greater than Grade 1. Some intra-patient dose escalation may occur.

A listing of BVD-523 administration, dispensed, missed/interrupted dose, intra-patient dose escalations, returned, and compliance will also be provided.

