10.1 EXPOSURE TO STUDY DRUG

Descriptive statistics will be provided for the total (cumulative) doses taken and total duration of treatment by treatment group for each study part. The total duration of treatment is calculated as (treatment stop date – treatment start date) + 1. If treatment stop date is missing, the date of final clinic visit will be used. By subject listing of study drug exposure will also be presented by study part and treatment group for each treatment cycle and all cycles combined.

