- \geq Grade 3 non-hematologic toxicity, except untreated nausea, vomiting, constipation, pain, and rash (these become DLTs if the AE persists despite adequate treatment), a doubling of AST/ALT in patients with grade 2 ALT/AST at baseline;
- A treatment interruption exceeding 5 days (or an interruption exceeding 7 days for rash, despite adequate treatment) in Cycle 1 (or inability to begin Cycle 2 for > 7 days) due to BVD-523-related toxicity³.

As specified in Section 2.1.1, the MTD is defined as the highest dose level at which $\leq 33\%$ of patients experience BVD-523 related DLTs in the first 21 days of treatment. The RP2D may be as high as the MTD and will be determined in discussion with the Clinical Investigators, the Medical Monitor, and the Sponsor. Observations related to pharmacokinetics (PK), pharmacodynamics (PD), and any cumulative toxicity observed after multiple cycles may be included in the rationale supporting the RP2D. Pharmacokinetic, pharmacodynamics, and/or Holter measurements may be suspended pending review of accumulated patient experience.

Treatment Emergent Adverse Event

A treatment emergent adverse event (TEAE) is any AE temporally associated with the use of BVD-523 (from BVD-523 initiation until 30 calendar days after the last administration of BVD-523), whether or not considered related to the study drug. If the onset of an AE is missing and the AE resolution date is either after the initial BVD-523 dose date or missing, then the AE will be considered treatment emergent.

AE Summaries

A subject who reported multiple AEs that map to a common PT or SOC is counted only once for that PT or SOC at the highest severity reported and at the greatest relationship to study drug.

The number and percentage of subjects who experienced at least one AE will be tabulated by SOC and PT with respect to dose level/treatment group for each study part. The same tabulation will also be applied to any SAE, any AE leading to premature discontinuation from the study, treatment emergent AEs and treatment-emergent SAEs.

³ For Amendments 1 and 2: A treatment interruption exceeding 3 days in Cycle 1 due to drug-related toxicity (or inability to begin Cycle 2 for > 7 days) due to drug-related toxicity.

For Amendment 3: A treatment interruption exceeding 5 days in Cycle 1 due to drug-related toxicity (or inability to begin Cycle 2 for > 7 days due to drug-related AE)

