14 TABLE OF CONTENTS FOR DATA DISPLAYS

TFL Shells are included as stand-alone documents.

Tables/Figures

Part I

Part I: Study Population

Part I - Table 14.1.1.1	Subject Disposition	ITT Population
Part I - Table 14.1.1.2	Analysis Population	ITT Population
Part I - Table 14.1.2	Protocol Deviations	ITT Population
Part I - Table 14.1.3.1	Demographic and Baseline Characteristics	Safety Population
Part I - Table 14.1.3.2	Demographic and Baseline Characteristics	ITT Population
Part I - Table 14.1.4.1	Prior Medications	Safety Population
Part I - Table 14.1.4.2	Concomitant Medications	Safety Population
Part I - Table 14.1.4.3	Concomitant Medication Taken for Adverse Events	Safety Population
Part I - Table 14.1.5.1	Treatment Compliance	Safety Population
Part I - Table 14.1.5.2	Exposure to Study Drug	Safety Population
Part I - Table 14.1.6	Pregnancy Test Results	Safety Population

Part I: Efficacy

Part I - Table 14.2.1	Target Lesion Response per RECIST 1.1	PP Population
Part I - Table 14.2.2	Non-Target Lesion Response per RECIST 1.1	PP Population
Part I - Table 14.2.3	New Lesion	PP Population
Part I - Table 14.2.4	Overall Response per RECIST 1.1	PP Population
Part I - Table 14.2.5	Best Overall Response per RECIST 1.1	PP Population
Part I - Table 14.2.6	Best Overall Response by Disease and Mutation Status	PP Population
Part I - Table 14.2.7	Duration of Best Overall Response by Disease and Mutation Status	PP Population

Part I: Safety

Part I - Table 14.3.1.1	Dose Limiting Toxicities	Safety Population
Part I - Table 14.3.1.2	Details of Dose Limiting Toxicities	Safety Population
Part I - Table 14.3.1.3	Doses Selected as MTD and RP2D	Safety Population
Part I - Table 14.3.1.4.1	Frequency and Reasons for Dose Delays/Interruptions	Safety Population
Part I - Table 14.3.1.4.2	Duration of Dose Delays/Interruptions	Safety Population
Part I - Table 14.3.1.5	Adverse Events	Safety Population
Part I - Figure 14.3.1.5	Bar Graph of Adverse Events	Safety Population
Part I - Table 14.3.1.6	Serious Adverse Events	Safety Population
Part I - Figure 14.3.1.6	Bar Graph of Serious Adverse Events	Safety Population
Part I - Table 14.3.1.7	Adverse Events Leading to Premature Discontinuation from the Study	Safety Population
Part I - Figure 14.3.1.7	Bar Graph of Adverse Events Leading to Premature Discontinuation from the Study	Safety Population
Part I - Table 14.3.1.8	Adverse Events by Relationship to Study Drug	Safety Population

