Part II - Figure 14.2.1	Genetic Information Leading to Target Lesion Response	PP Population
Part II - Table 14.2.2	Non-Target Lesion Response per RECIST 1.1	PP Population
Part II - Table 14.2.3	New Lesion	PP Population
Part II - Table 14.2.4	Overall Response per RECIST 1.1	PP Population
Part II - Table 14.2.5	Best Overall Response per RECIST 1.1	PP Population
Part II - Figure 14.2.6	Genetic Information Leading to Best Overall Response	PP Population
Part II - Table 14.2.7	Best Overall Response by Disease and Mutation Status	PP Population
Part II - Table 14.2.8	Duration of Best Overall Response by Disease and Mutation Status	PP Population
Part II: Safety		
Part II - Table 14.3.1.1	Dose Limiting Toxicities	Safety Population
Part II - Table 14.3.1.2	Details of Dose Limiting Toxicities	Safety Population
Part II - Table 14.3.1.3	Duration of Dose Interruptions	Safety Population
Part II - Table 14.3.1.3	Adverse Events	Safety Population
Part II - Figure 14.3.1.4.1	Bar Graph of Adverse Events by PT	Safety Population
Part II - Figure 14.3.1.4.2	Bar Graph of Adverse Events by SOC and PT	Safety Population
Part II - Table 14.3.1.5	Serious Adverse Events	Safety Population
Part II - Figure 14.3.1.5.1	Bar Graph of Serious Adverse Events by PT	Safety Population
Part II - Figure 14.3.1.5.2	Bar Graph of Serious Adverse Events by SOC and PT	Safety Population
Part II - Table 14.3.1.6	Adverse Events Leading to Premature Discontinuation from the Study	Safety Population
Part II - Figure 14.3.1.6.1	Bar Graph of Adverse Events Leading to Premature Discontinuation from the Study by PT	Safety Population
Part II - Figure 14.3.1.6.2	Bar Graph of Adverse Events Leading to Premature Discontinuation from the Study by SOC and PT	Safety Population
Part II - Table 14.3.1.7	Adverse Events by Relationship to Study Drug	Safety Population
Part II - Figure 14.3.1.8.1-1	Bar Graph of Probably Related Adverse Events by PT	Safety Population
Part II - Figure 14.3.1.8.1-2	Bar Graph of Possibly Related Adverse Events by PT	Safety Population
Part II - Figure 14.3.1.8.1-3	Bar Graph of Unrelated Adverse Events by PT	Safety Population
Part II - Figure 14.3.1.8.2-1	Bar Graph of Probably Related Serious Adverse Events by PT	Safety Population
Part II - Figure 14.3.1.8.2-2	Bar Graph of Possibly Related Serious Adverse Events by PT	Safety Population
Part II - Figure 14.3.1.8.2-3	Bar Graph of Unrelated Serious Adverse Events by PT	Safety Population

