- Part I – Listing 16.2.1.8.4 Concomitant Medication Taken for Adverse Events
- Part I – Listing 16.2.1.9 On Study Procedures
- Part I – Listing 16.2.1.10.1 Treatment Compliance
- Part I – Listing 16.2.1.10.2 Exposure to Study Drug
- Part I – Listing 16.2.1.10.3 BVD-523 Dose History

Efficacy

- Part I – Listing 16.2.2.1 Target Lesions
- Part I – Listing 16.2.2.2 Non-Target Lesions
- Part I – Listing 16.2.2.3 New Lesions
- Part I – Listing 16.2.2.4 Tumor Response per RECIST 1.1
- Part I – Listing 16.2.2.5 Tumor Measurements over Time

Safety

- Part I – Listing 16.2.3.1 DLTs, MTD, and RP2D
- Part I – Listing 16.2.3.2 Relationship of MedDRA System Organ Class and Preferred Term with Verbatim
- Part I – Listing 16.2.3.3.1 Adverse Events
- Part I – Listing 16.2.3.3.2 Adverse Events Leading to Early Discontinuation from the Study
- Part I – Listing 16.2.3.3.3 Adverse Events Leading to Study Drug Interruptions and Length of Interruptions
- Part I – Listing 16.2.3.3.4 Adverse Events Leading to Study Drug Dose De-escalations
- Part I – Listing 16.2.3.4 Serious Adverse Events

Laboratory Results

Part I – Listing 16.2.4.1.1 Laboratory Evaluations – Hematology

Part I – Listing 16.2.4.1.2 Laboratory Evaluations – Hematology, Abnormal and Clinically Significant

Part I – Listing 16.2.4.2.1 Laboratory Evaluations – Clinical Chemistry

Part I – Listing 16.2.4.2.2 Laboratory Evaluations – Clinical Chemistry, Abnormal and Clinically Significant

Part I – Listing 16.2.4.3.1 Laboratory Evaluations – Urinalysis

Part I – Listing 16.2.4.3.2 Laboratory Evaluations – Urinalysis, Abnormal and Clinically Significant

Physical Examinations Results

Part I – Listing 16.2.5.1 Physical Examinations

Part I – Listing 16.2.5.2 ECOG Performance Status

Part I – Listing 16.2.5.3 Electrocardiograms

Part I – Listing 16.2.5.4 Holter Monitoring

Part I – Listing 16.2.5.5 Holter Monitoring Finding

Part I – Listing 16.2.5.6 Ophthalmology Examinations

Part I – Listing 16.2.5.7 Vital Signs

Part I – Listing 16.2.5.8 Pregnancy Results

Pharmacokinetics

Part I – Listing 16.2.6.1 Pharmacokinetic Concentration Measured from Blood Samples

Part I – Listing 16.2.6.2 Pharmacokinetic Concentration Measured from Urine Samples

Part I – Listing 16.2.6.3 Pharmacokinetic Parameters

Pharmacodynamics

Part I – Listing 16.2.7.1 Fluid/Blood Pharmacodynamics

Part I – Listing 16.2.7.2 Tissue Pharmacodynamics

Tumor Genotyping

Part I – Listing 16.2.8 Tumor Genetic or Genotyping Information / Result

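### Part II has no planned summary of dose reductions from the RP2D, and the discontinuation AE tables count study exit where the protocol specifies stopping the drug

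*SAP*

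**What the plan says.** SAP 3.1 states for Part 2: "Intra-patient dose modifications are allowed, including dose reductions/interruptions as needed and re-escalations up to and including RP2D", at the investigator's discretion. Protocol Section 8 says the same. For resumption after a DLT or unacceptable toxicity, it mentions the next lower dose level tested or a decrease of 20–30%.

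The planned outputs that bear on dose changes are these:

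- SAP 8.7 (text): "A listing of BVD-523 administration, dispensed, missed/interrupted dose, intra-patient dose escalations, returned, and compliance will also be provided". Reductions are not named.
- SAP 10.1 (text): descriptive statistics for cumulative doses taken and duration of treatment. The definition of duration begins "The total duration of treatment is calculated as (treatment stop date"; it subtracts the start date and adds 1.
- SAP 14, Part I: Table 14.3.1.4.1, "Frequency and Reasons for Dose Delays/Interruptions"; a companion table of durations (14.3.1.4.2); and Listing 16.2.3.3.4, "Adverse Events Leading to Study Drug Dose De-escalations".
- SAP 14, Part II: Table 14.3.1.3, "Duration of Dose Interruptions", and a listing of AEs leading to interruptions.

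On discontinuation, Protocol 10.3.9 says that "AEs leading to discontinuation of trial medication will be summarized by primary system organ class (SOC) and preferred terms". SAP 10.2 instead tabulates "any AE leading to premature discontinuation from the study", and the tables in SAP 14 for both parts carry that wording.

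**The concern.** The RP2D is a primary endpoint. Protocol 3.1.4.3 allows cumulative toxicity over several cycles to count in choosing it, and Protocol 3.1.3 says such toxicity may lead to later dose reductions or affect the RP2D. DLTs are counted only in the first 21 days. After that, reductions, interruptions and permanent stops are important evidence on whether patients can stay on the dose. Reductions do happen: Protocol 1.4 reports them for rash, gastrointestinal effects, raised AST/ALT and raised creatinine.

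Part 2 plans up to about 105 evaluable patients at the RP2D. SAP 2.2 describes the groups as dosed at the RP2D, and SAP 9 tabulates response by group. No planned table shows how many patients in a group were still taking that dose. A reader of the study report could take both the tolerability and the responses as belonging to a dose that some patients had left.

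**Working it through.** The documents give no figure on Part 2 dose modification to reproduce. The check is a comparison of outputs, followed by a test of whether the exposure table could stand in for the missing ones.

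**Step 1. Outputs side by side (SAP 14 titles)**

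| Output | Part I | Part II |
|---|---|---|
| Frequency and reasons for interruptions, table | 14.3.1.4.1 | none |
| Duration of interruptions, table | 14.3.1.4.2 | 14.3.1.3 |
| AEs leading to interruption, listing | 16.2.3.3.3 | 16.2.3.3.3 |
| AEs leading to de-escalation, listing | 16.2.3.3.4 | none |
| Number of patients with a dose reduction, table | none by title | none by title |
| Patient-level dose history, listing | 16.2.1.10.3 | 16.2.1.10.3 |

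No reason is given for the two omissions. The Part II list also uses the number 14.3.1.3 for two different tables, so an editing slip is possible.

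**Step 2. What the exposure table can show**

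Inputs: a reduction of 20–30% (Protocol Section 8). Assumptions: full dose for 21 days, reduced dose from Day 22 to the end, no missed doses, and T total treatment days.

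Full-dose-equivalent days: F = 21 + (T − 21) × (1 − r). Relative dose intensity (RDI) = F / T. Missed full-dose days giving the same cumulative dose and the same duration: T − F.

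| T (assumed) | r | F | RDI | Equivalent missed days |
|---|---|---|---|---|
| 42 | 20% | 37.8 | 90% | 4.2 |
| 42 | 30% | 35.7 | 85% | 6.3 |
| 63 | 20% | 54.6 | 87% | 8.4 |
| 63 | 30% | 50.4 | 80% | 12.6 |
| 126 | 20% | 105.0 | 83% | 21.0 |
| 126 | 30% | 94.5 | 75% | 31.5 |

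For T = 126 and r = 20%: 21 + 105 × 0.80 = 105; 105/126 = 83%; 126 − 105 = 21. For r = 30%: 21 + 105 × 0.70 = 94.5; 94.5/126 = 75%; 126 − 94.5 = 31.5.

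Duration is T in both cases, because it runs from start date to stop date. The two columns of the exposure table therefore match for a patient who was reduced and one who missed doses at full strength. This assumes that cumulative dose is in mg. If it is a count of doses, a reduced patient who missed none shows 126 × 2 = 252, the same as a patient never reduced.

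**Step 3. Time outside the DLT window**

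(T − 21)/T is 50% at 42 days, 67% at 63 days and 83% at 126 days.

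**Step 4. Discontinuation wording**

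Protocol 10.3.9 is keyed to stopping the drug, SAP 10.2 to leaving the study. Protocol 5.2.6 and 5.2.7 place an End of Treatment visit and a 30-day safety contact after the last dose, so the two events are not identical by definition. SAP 15 explains its departure from the protocol's mITT definition but does not mention this one.

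**The case against.** The strongest reply is that the data are not lost. Part II has a dose history listing. SAP 10.1 adds a by-subject exposure listing for each cycle, SAP 6.6 lists all collected data, and Protocol 9.3 has the action taken recorded for every AE. Part II also tabulates compliance, cumulative dose and interruption duration, so a group with many reductions need not look the same as one at full dose. This stands, and it limits the point to what is summarised. It does not supply a rate of reduction by group, or the reasons. SAP 8.7 gives no formula for compliance, so it is unclear whether a reduced patient would count as fully compliant.

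A second reply is that leaving the study and stopping the drug nearly coincide here. Protocol 7.2 makes unacceptable toxicity a reason for withdrawal from the study, follow-up after the last dose is short, and the disposition table counts unacceptable toxicity. The overlap may well be large, but the SAP does not say that the two are treated as the same.

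A third is that the RP2D is fixed from Part 1 data, with the Safety Monitoring Committee reviewing later-cycle toxicity. That is true of decisions during the trial. It does not replace the summary in the final report.

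A reader might infer that Part II tabulates AEs only if they end study participation. It does not: all AEs, SAEs and treatment-emergent AEs are tabulated, with severity and relationship also shown for AEs, and with no cut-off at Day 21. A reader might also picture a long drug-free gap straight after Day 21 that no table would show. Such a gap would belong in the interruption table, and a drug-related delay of more than 7 days in starting Cycle 2 is itself a DLT criterion.

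**Conclusion.** Two gaps hold on the text. Part II has no table, by title, and no dedicated AE listing for dose reductions, and it lacks two dose-modification outputs planned for Part I. The SAP also replaces the protocol's summary of AEs leading to discontinuation of trial medication with one on discontinuation from the study, without acknowledging the change.

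Tolerability of the RP2D beyond Cycle 1 is therefore incompletely summarised and could look better than it was. A reader might go further and conclude that it is overstated. The documents do not support that: they give no Part 2 rates of reduction or discontinuation, so neither the direction nor the size of any distortion can be computed. The dose intensities of 83–75% illustrate what the exposure table cannot distinguish. They rest on an assumed 126 days and an assumed reduction from Day 22, and are not estimates for this trial.

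The absence of outputs is read from titles. SAP 14 says that the table shells are stand-alone documents, and they could not be checked. The point should be addressed before the Part 2 outputs are produced; it does not affect patient management.

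**What to change.** In SAP 8.7, 10.1, 10.2 and 14:

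1. For Part II, by group and overall, restore the table of frequency and reasons for delays and interruptions, and restore the listing of AEs leading to dose de-escalation.
2. For Part II, by group and overall, add the number and percent of patients with at least one AE-related dose reduction, with reasons, and the relative dose intensity: cumulative mg / (RP2D × 2 × days from first to last dose). State that cumulative dose is in mg.
3. In both parts, define the discontinuation AE table by action taken, study drug permanently stopped, so that it delivers what Protocol 10.3.9 specifies.

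The cost is SAP wording and a little extra programming. Part I provides models for item 1. Dosing dates and times (Protocol 8.1.2) and AE action taken (Protocol 9.3) are already collected, so no new data are needed. Relative dose intensity is an addition that neither document promises; the rest aligns Part II with Part I and the SAP with the protocol.

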8.8 PROTOCOL DEVIATIONS

Protocol deviations in the following areas will be collected from the study:

- drug dosing,
- exclusion criteria,
- general protocol issues,
- informed consent form issues,
- inclusion criteria,
- missed study procedure,
- SAE issues,
- visit windows,
- other, and
- unknown.

Impacts of the above protocol deviations on the analysis population will be determined by study team before study closure and documented in the SAP.

The frequency and percentage of patients with each protocol deviation along with the impact on the analysis population will be presented by treatment group and overall for each study part using the ITT Population. A listing of patients with protocol deviation(s) will also be provided.

